16.4 Vaccine Response Analysis

Unless otherwise stated, vaccine response analyses will be performed on the mITT population, and where appropriate on the ITT.

16.4.1 Definition of Primary Vaccine Response Endpoint

The primary endpoint for this study is the proportion of subjects with a positive serum IgG response to tetanus toxoid at Week 16 (4 weeks post-vaccination), defined as:

1. ≥ 4 -fold increase in anti-tetanus IgG concentration from baseline in subjects with pre-vaccination anti-tetanus IgG concentrations ≥ 0.1 IU/mL, OR
2. ≥ 0.2 IU/mL anti-tetanus IgG concentrations in subjects with pre-vaccination anti-tetanus IgG concentrations < 0.1 IU/mL.

Subjects in receipt of systemic rescue medication will not be vaccinated, and so will thus not be included in the mITT. Thus, for the primary analysis of the primary vaccine response endpoint, no imputation is required as all subjects included in the mITT are required to have an evaluable vaccine (IgG) response.

16.4.2 Analysis of Primary Vaccine Response Endpoint

The estimate of the corresponding proportion for the endpoint will be adjusted for the randomization strata baseline **CCI** using the Cochran-Mantel-Haenszel (CMH) estimate of the risk difference and corresponding 2-sided 90% CI. This primary analysis will be conducted on the mITT population.

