As the anti-tetanus IgG titer of ≥ 0.1 IU/mL is generally recognized as seroprotective, the primary endpoint was defined for subjects with and without existing pre-vaccination seroprotective titers. Response for subjects with existing anti-tetanus IgG (≥ 0.1 IU/mL) at baseline was defined as a 4-fold increase in anti-tetanus IgG titer from baseline, indicative of a booster response. Response for subjects without existing IgG (< 0.1 IU/mL) was defined as 0.2 IU/mL, a concentration 2-fold higher than the recognized seroprotection level. As subjects with already high anti-tetanus IgG titers at baseline may not achieve a 4-fold increase in IgG following vaccination, a secondary endpoint identical to the primary endpoint but with response defined as a 2-fold increase in titer for subjects with pre-existing anti-tetanus IgG was also included.

This document is confidential.

Page 42 of 133

A follow-up visit is scheduled for subject safety and will occur at the Week 24 visit (12 weeks after the last dose of study medication). The duration of the follow-up period corresponds to approximately 5 half-lives of nemolizumab, which is considered adequate to ensure subject safety.

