# 3. Study Objectives

## 3.1. Primary Objective

The primary objective is to assess the effect of nemolizumab (CD14152) on humoral immune responses to tetanus and meningococcal vaccination in adult and adolescent subjects with moderate-to-severe atopic dermatitis (AD).

The main estimand for primary objective is listed as below:

Primary	The proportion of subjects with a positive serum IgG response to tetanus toxoid at	
Endpoint	Week 16 (4 weeks post-vaccination) defined as:	
	≥ 4-fold increase in anti-tetanus IgG concentrations from baseline in subjects with pre-vaccination anti-tetanus IgG concentrations ≥ 0.1 IU/mL	
	OR	
	≥ 0.2 IU/mL anti-tetanus IgG concentrations in subjects with pre-vaccination anti-tetanus IgG concentrations < 0.1 IU/mL	
Population	Of all defined by the study inclusion / exclusion criteria, the analysis population will include all randomized subjects who received at least one dose of study drug and vaccine injection, have an evaluable vaccine response and did not receive any systemic rescue therapy prior to the post-vaccination vaccine response assessment (mITT population).	
Primary endpoint will be analyzed by the Cochran-Mantel-Haenszel (CMH) esti of the risk difference and corresponding 2-sided 90% CI, adjusted for randomization stratum baseline CCI using weight average of stratum-specific proportion.		
Intercurrent Event	None	

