#### 6.2. Key Definitions

#### 6.2.1. Baseline

Unless otherwise stated, the baseline value for any variable will be the last non-missing value taken prior to the receipt of study treatment at the Baseline visit (Day 1). The receipt of study treatment is defined as the 1st injection of study drug if it exists. Otherwise, baseline is defined as the last value taken prior to the randomization.

For diary data (CCI), the baseline values will be derived from data collected during the 7 days prior to the first administration of study drug, if it exists. Otherwise, the data collected during 7 days prior to randomization will be used. Baseline score will be the weekly prorated average of non-missing subject diary scores reported during the 7 days. A minimum of 4 daily scores out of the 7 days is required to calculate the weekly prorated average score.

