# 8. Vaccine Response Analysis

## 8.1. Primary Vaccine Response Endpoint and Analysis

# **8.1.1.** Primary Analysis of Primary Endpoint

The primary endpoint of this study is the proportion of subjects with a positive serum IgG response to tetanus toxoid at Week 16 (4 weeks post-vaccination), defined as:

- ≥ 4-fold increase in anti-tetanus IgG concentrations from baseline in subjects with pre-vaccination anti-tetanus IgG concentrations ≥ 0.1 IU/mL, OR
- ≥ 0.2 IU/mL anti-tetanus IgG concentrations in subjects with pre-vaccination anti-tetanus IgG concentrations < 0.1 IU/mL

Anti-tetanus IgG concentrations and the ratio from baseline will be summarized by treatment group and by visit using descriptive statistics.

The analysis for primary endpoint will be using the Cochran-Mantel-Haenszel (CMH) estimate of the risk difference and corresponding 2-sided 90% CI. It will be adjusted for the randomization stratum baseline using weighted average of stratum-specific proportion using CMH.

The example SAS code for CMH model is included in Section 20.1. The primary analysis will be conducted on the mITT population.

Subjects in receipt of systemic rescue medication will not be vaccinated. As the primary analysis will be conducted on the mITT, no imputation is required.

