14.2.2.4.9	Sensitivity Analysis of Proportion of Subjects with Positive Serum Bactericidal Antibody Response to Meningococcal Serogroup C Polysaccharide at Week 16 – Observed Case – Non-Imputed Values	ITT
14.2.2.4.10	Sensitivity Analysis of Proportion of Subjects with Positive Serum Bactericidal Antibody Response to Meningococcal Serogroup C Polysaccharide at Week 16 – COVID-19 Affected Case – Non-Imputed Values	ITT
14.2.2.5.1	Analysis of Proportion of Subjects with Positive Serum Bactericidal Antibody Response to Meningococcal Serogroup C Polysaccharide using Different Criteria at Week 16 – Non-Imputed Values	mITT
14.2.2.5.2	Sensitivity Analysis of Proportion of Subjects with Positive Serum Bactericidal Antibody Response to Meningococcal Serogroup C Polysaccharide using Different Criteria at Week 16 – Missing as Non-Responder – Non-Imputed Values	ITT
14.2.2.5.3	Sensitivity Analysis of Proportion of Subjects with Positive Serum Bactericidal Antibody Response to Meningococcal Serogroup C	ITT

	Polysaccharide using Different Criteria at Week 16 – Observed Case – Non- Imputed Values	
14.2.2.5.4	Sensitivity Analysis of Proportion of Subjects with Positive Serum Bactericidal Antibody Response to Meningococcal Serogroup C Polysaccharide using Different Criteria at Week 16 – COVID-19 Affected Case – Non-Imputed Values	ITT
14.2.2.6.1	Analysis of Proportion of Subjects with Positive Serum Bactericidal Antibody Response to Meningococcal Serogroup C Polysaccharide using Different Criteria at Week 16 – Imputed Values	mITT
14.2.2.6.2	Sensitivity Analysis of Proportion of Subjects with Positive Serum Bactericidal Antibody Response to Meningococcal Serogroup C Polysaccharide using Different Criteria at Week 16 – Missing as Non-Responder – Imputed Values	ITT
14.2.2.6.3	Sensitivity Analysis of Proportion of Subjects with Positive Serum Bactericidal Antibody Response to Meningococcal Serogroup C Polysaccharide using Different Criteria at Week 16 – Observed Case – Imputed Values	ITT
14.2.2.6.4	Sensitivity Analysis of Proportion of Subjects with Positive Serum Bactericidal Antibody Response to Meningococcal Serogroup C Polysaccharide using Different Criteria at Week 16 – COVID-19 Affected Case – Imputed Values	ITT
14.2.2.7.1	Analysis of Geometric Mean Concentration of Anti-tetanus IgG at Baseline and Week 16	mITT
14.2.2.7.2	Sensitivity Analysis of Geometric Mean Concentration of Anti-tetanus IgG at Baseline and Week 16 – Observed Case	ITT

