# 18. Index of Figures

Figure Number	Name	Analysis Set
14.1.1.4	Time (days) to Permanent Discontinuation of Study Drug by Reason for Discontinuation	Subjects who Discontinued from Study Drug – ITT
14.2.1.1.5	Forest Plot for Proportion of Subjects with a Positive IgG Response to Tetanus Toxoid at Week 16	mITT
14.2.1.1.6	Plot of Individual Anti-tetanus IgG Concentrations at Baseline and Week 16– Observed Case	mITT
14.2.1.1.7	Plot of Fold Change in Anti-tetanus IgG Concentration Between Baseline and Week 16- Observed Case	mITT
14.2.2.1.5	Forest Plot for Proportion of Subjects with a Positive IgG Response to Tetanus Toxoid at Week 16 using Different Criteria	mITT
14.2.2.2.5	Forest plot for Proportion of Subjects with Serum Anti-tetanus IgG Concentrations of ≥ 0.1 IU/mL at Week 16	mITT
14.2.2.3.5	Forest plot for Proportion of Subjects with Serum Anti-tetanus IgG Concentrations of ≥ 1.0 IU/mL at Week 16	mITT
14.2.2.4.5	Forest plot for Proportion of Subjects with Positive Serum Bactericidal Antibody Response to Meningococcal Serogroup C Polysaccharide at Week 16 – Imputed values	mITT
14.2.2.4.6	Plot of Fold Change in Serum Bactericidal Assay Reciprocal Titer Between Baseline and Week 16– Observed Case – Imputed values	mITT
14.2.2.4.11	Forest plot for Proportion of Subjects with Positive Serum Bactericidal Antibody Response to Meningococcal Serogroup C Polysaccharide at Week 16 – Non-Imputed values	mITT
14.2.2.4.12	Plot of Fold Change in Serum Bactericidal Assay Reciprocal Titer Between Baseline and Week 16– Observed Case – Non-Imputed values	mITT
14.2.2.5.5	Forest plot for Proportion of Subjects with Positive Serum Bactericidal Antibody Response to Meningococcal Serogroup C Polysaccharide using different criteria at Week 16 – Non-imputed values	mITT
14.2.2.5.6	Plot of Individual Serum Bactericidal Assay Reciprocal Titer at Baseline and Week 16– Observed Case – Non-imputed values	mITT
14.2.2.6.5	Forest plot for Proportion of Subjects with Positive Serum Bactericidal Antibody Response to Meningococcal Serogroup C Polysaccharide using different criteria at Week 16 – Imputed values	mITT
14.2.2.6.6	Plot of Individual Serum Bactericidal Assay Reciprocal Titer at Baseline and Week 16– Observed Case – Imputed values	mITT
14.2.4.1.2	Individual Subject Nemolizumab Time-Concentration Profiles by Visit	PK
14.2.4.1.3 CCI	Mean Nemolizumab Time-Concentration Profiles by Visit	PK

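### The primary risk difference is adjusted only for baseline severity, although baseline anti-tetanus IgG is part of the responder rule; the analysis is valid but may give up precision against the 10-point margin

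*Protocol*

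**What the plan says.** Protocol 16.4.2 sets the primary analysis as a CMH risk difference with a 2-sided 90% CI in the mITT: "The estimate of the corresponding proportion for the endpoint will be adjusted for the randomization strata baseline" severity. The scale is blacked out; the synopsis gives its levels as moderate and severe. SAP 8.1.1 repeats the method, "using weighted average of stratum-specific proportion using CMH", as does the estimand table in SAP 3.1, "using weight average of stratum-specific proportion". No other covariate is named in the readable text.

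On baseline IgG:

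- Protocol 16.4.1 counts a response as a 4-fold rise from baseline when the pre-vaccination value is at least 0.1 IU/mL, and as at least 0.2 IU/mL otherwise.
- SAP 6.2.1 defines baseline, by default, as the last value before the first dose on Day 1.
- SAP 17 lists "Analysis of Geometric Mean Concentration of Anti-tetanus IgG at Baseline and Week 16" and SAP 18 lists "Plot of Individual Anti-tetanus IgG Concentrations at Baseline and Week 16".
- Protocol 7.2 notes that "subjects with already high anti-tetanus IgG titers at baseline may not achieve a 4-fold increase in IgG following vaccination", and adds a 2-fold secondary endpoint for that reason.

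Protocol 16.9 and SAP 3.5 size the study at about 245 (about 123 per arm) so that the 90% CI excludes a difference of more than 10 points.

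**The concern.** The trial's answer depends on the width of one confidence interval. The plan stratifies that interval by skin disease severity, which has no stated link to tetanus response, and leaves out a pre-dose laboratory value that its own text links to response. If baseline IgG explains part of the outcome variance, stratifying on it narrows the interval with the same subjects and data. The 2-fold, 0.1 and 1.0 IU/mL endpoints, the geometric means and the plots help interpretation, but none of them narrows the primary interval. Bias, coverage and type I error are not in question.

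**Working it through.** **The plan's own figure.** The 123 per arm cannot be reproduced, because no response rate, power or attrition allowance is stated. It can be inverted. With equal true rates p, margin 0.10 and one-sided 5%:

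n = (1.645 + 0.842)² × 2p(1−p) / 0.10²

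At p = 0.888 this gives 123, so 123 per arm has 80% power on a one-sided reading only if response is about 89%. At p = 0.80 the half-width is 1.645 × √(2 × 0.80 × 0.20 / 123) = 8.4 points, and the chance of excluding −10 is 62%.

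**Assumed inputs** (none are in the documents):

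- 105 evaluable per arm, about 15% below 123; true difference 0; 40% severe.
- log10 baseline IgG normal, mean −0.2, SD 0.45. This puts about 4%, 63% and 33% of subjects in the bands <0.1, 0.1 to <1.0 and >=1.0 IU/mL. An alternative mean of −0.52 gives 14%, 73% and 12%.
- log10 Week 16 IgG linear in log10 baseline, residual SD 0.35, slope 0.3 (strong gradient), 0.5 (moderate) or 0.8 (Week 16 tracks baseline closely). The intercept is set for 90% or 76% response.
- Responder rule as in Protocol 16.4.1; Mantel-Haenszel risk difference with Sato variance for both analyses; 20,000 simulated trials per scenario.

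**Hand check.** The share of outcome variance lying between bands is R² = Σ w_k (p_k − p)² / [p(1−p)]. For the moderate gradient the band rates are 99.9/96/78% with weights 0.038/0.634/0.328, so p = 0.902 and R² = 8.4%. The strong gradient at 90% response (100/97/75%) gives 12.0%, the strong gradient at 76% (99.9/89/49%) gives 20.3%, and close tracking (98/92/85%) gives 1.5%. The simulated gains are slightly smaller because extra strata cost a little precision.

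**Simulated results, 105 per arm** (severity-only to severity × IgG band):

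| Scenario | Variance reduction | 90% CI half-width, points | P(lower limit > −10) |
|---|---|---|---|
| 90% response, moderate | 6–7% | 6.8 to 6.5 | 78% to 80% |
| 90%, strong | 11% | 6.8 to 6.4 | 78% to 82% |
| 90%, moderate, mean −0.52 | 7–8% | 6.8 to 6.5 | 78–79% to 81% |
| 76%, strong | about 19% | 9.7 to 8.7 | 52–53% to 59–60% |
| 90%, close tracking | none | unchanged | unchanged |

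Closed-form check of row 1: SE = √(2 × 0.9 × 0.1 / 105) = 0.0414, and Φ(0.10/0.0414 − 1.645) = 78%. With 6.7% less variance the SE is 0.0400 and the probability is 80%.

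**Equivalent subjects.** 105 / (1 − 0.065) = 112, about 7 more per arm; 105 / (1 − 0.19) = 130, about 25 more.

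**If both limits must lie within ±10 points,** the chance goes from 56% to 61% (90%, moderate) and from 5% to 19% (76%, strong), and stays at 56% with close tracking.

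**Validity.** Coverage of the 90% CI was 0.891–0.902 with severity only and 0.892–0.903 with bands. At a true difference of −10, the margin was falsely excluded in 4.8–5.5% and 4.7–5.8% of trials.

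**ITT non-responder analysis** (123 per arm, 15% non-evaluable). The variance reduction ranged from −0.8% to 1.8% (90%, moderate), 3.5% to 10.3% (76%, strong) and −1.5% to 0.9% (90%, close tracking).

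**The case against.** The strongest reply is that the planned analysis has no defect. It adjusts for the factor used in randomization, and adding a prognostic stratifier is optional. The benefit also rests on inputs that the documents do not supply. The residual SD matters in particular: with a moderate slope and 90% response, raising it from 0.35 to 0.5 or 0.6 shrinks the variance reduction to 2.8% or 1.9%, and at slope 0.8 with SD 0.5 the variance rises by 0.7%. The largest gains assume 76% response, where the trial would be underpowered anyway. All of this stands, and it puts the honest range at about zero to 20%. It does not show a material loss from adjusting.

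Two further points concern what can be read. The schedule of assessments is blacked out and the responder rule says pre-vaccination, so Day 1 sampling is inferred from the baseline definition and the listed Baseline outputs. It is strongly implied but should be confirmed. If no Day 1 sample exists, the missing-value rule below places everyone in one band and returns the severity-only analysis. The example code in SAP 20.1 is also unavailable, so the planned variance formula is unknown; Sato is valid for either stratification.

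Finally, changing a protocol-specified primary analysis at SAP version 5.0, after a dry run, has a cost, and the 2-fold endpoint would then be analyzed differently from the primary. That is why the timing condition and the stated scope are needed.

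**Conclusion.** The point holds as a missed gain in precision, not an error. The readable plan adjusts the primary risk difference for severity alone and leaves out a pre-dose value that enters the endpoint and that Protocol 7.2 treats as limiting response. At about 90% response, near the rate at which 123 per arm gives 80% one-sided power, the likely gain is modest: about 7% of the variance and 2 percentage points of success probability for a moderate gradient, and 11% and 4 points for a strong one. It could be nil, or about 19% if response is nearer 76% with a strong gradient. These figures rest on the assumed titer model, 105 evaluable per arm and no true difference. The change is worth making if treatment codes are unreleased. Confidence in its size is medium.

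**What to change.** Before treatment codes are released, amend SAP 8.1.1 and the SAP 3.1 estimand table, and record the change from Protocol 16.4.2 in SAP section 14:

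- **Primary analysis:** CMH risk difference stratified by severity × Day 1 pre-first-dose anti-tetanus IgG band (<0.1, 0.1 to <1.0, >=1.0 IU/mL), with a 2-sided 90% CI from the Sato variance. The 0.1 cut comes from the responder rule and the 1.0 cut from a secondary endpoint, so neither is data-driven.
- **Sparse cells:** within a severity level, merge an outer band with no subjects in one arm into the middle band. This uses band and arm counts only, never outcomes.
- **Missing Day 1 IgG:** place the subject in the middle band. This can occur in the ITT. It can also occur in the mITT, although "all subjects included in the mITT are required to have an evaluable vaccine (IgG) response", because a Week 16 value below 0.2 IU/mL is non-response under either branch. Do not substitute a Week 12 value, which is post-randomization.
- **Scope:** the primary endpoint in the mITT and its three ITT sensitivity analyses. SAP 8.1.2 and Protocol 16.4.4 reuse the primary method by reference, so state that severity-only CMH stays for the subgroup forest plots, all secondary vaccine endpoints and the binary efficacy endpoints. Keep it also as an mITT sensitivity analysis of the primary endpoint.
- **If codes are already released:** report the banded result as supplementary only.

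The cost is one more SAP version and minor programming, with no new data. The downsides are little or no gain if the gradient is weak, little gain in the ITT non-responder analysis, and the need for the merge rule. That rule was triggered in 43–44% of simulated trials when 4% of subjects were below 0.1 IU/mL (2.5 subjects moved on average), and in 1–2% when 14% were (about 5.5 moved).

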16.4.3 Sensitivity Analyses of the Primary Vaccine Response Endpoint

Sensitivity analyses for the primary analysis of the primary endpoint will also be conducted in order to test for the robustness of the primary analysis. The primary analysis above will be repeated on the ITT population as sensitivity, whereby any subjects without an evaluable vaccine response will be regarded as a Non-Responder. Further to this, an observed case analysis on the ITT population will also be performed, with no imputation for missing data at Week 16.

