9.3 Measures to Minimize Bias: Study Treatment Assignment and Blinding

9.3.1 Method of Study Treatment Assignment

At the baseline visit, a unique randomization number will be assigned to an eligible subject via interactive response technology (IRT). Subjects will be randomized in a 1:1 ratio to receive either nemolizumab or placebo. The randomization scheme will be

This document is confidential.

stratified by baseline disease severity **CCI** to ensure appropriate distribution of assignment to the 2 treatment groups.

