9.7.1 Early Termination Visit

Subjects may discontinue from the study or discontinue the study treatment only and continue to participate in the study.

Subjects who prematurely discontinue from the study should undergo final study assessments according to the following guidelines:

- Subjects discontinued from the study during the treatment period on/before the Week 16 visit should attend an early termination visit.
- A follow-up/final visit is required 12 weeks after the last study drug administration.

Subjects who prematurely discontinue the study drug will be asked to continue participation in the study; however, subjects who discontinue the study drug prior to Week 12 should not be vaccinated. Subjects will be asked to return for all remaining visits and assessments (including daily assessment of pruritus, sleep disturbance, etc). Participation will continue until the subject completes the final study visit or otherwise discontinues study participation.

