16.9 Determination of Sample Size

Approximately 245 subjects will be randomized (~123 per arm) to show that the 90% confidence interval of the proportion difference between treatment groups will exclude a difference of more than 10%.

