# 6. General Aspects for Statistical Analysis

#### 6.1. General Methods

The statistical evaluation will be performed using SAS® software version 9.4 or higher (SAS Institute, Cary, NC). All data will be listed, and summary tables will be provided. Summary statistics will be presented by treatment group. Summaries will be presented for each treatment and overall for Demographic, Other Baseline Characteristics and Medication. For all other analyses, summaries will be presented for each treatment.

Continuous variables will be summarized using the number of observations (n), mean, standard deviation (SD), median, minimum, and maximum by treatment group. Categorical variables will be summarized using number of observations (n), frequency and percentages of subjects for each category by treatment group.

All statistical tests on the vaccine response endpoints will be conducted at the 2-sided 10% level and the 90% CI will be estimated. For all other endpoints, the statistical tests will be conducted at the 2-sided 5% level and the 95% CI will be estimated.

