#### **8.1.2.** Sensitivity Analysis of Primary Endpoint

Three sensitivity analyses will be performed on ITT population and the same statistical testing as the primary analysis will be performed:

- Non-responder Imputation: any subjects without an evaluable vaccine response will be
  regarded as a Non-Responder. Non-evaluable vaccine response: defined as a response that
  cannot be classified as positive or negative due to missing assessment for the endpoint.
- **Observed Case**: No data will be imputed. All data as observed will be included in the analysis and the percentage will be calculated based on the number of observation available.
- COVID-19 Affected Case: Removal of subjects with COVID-19 (i.e. exclusion of subjects who
  had COVID-19).

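### The ITT non-responder sensitivity analysis scores subjects barred from vaccination as vaccine failures, so it measures retention and response together and is not a conservative check of a no-impairment result

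*Protocol*

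**What the plan says.** The primary analysis uses the mITT: randomized subjects who received study drug and vaccine, have an evaluable response, and had no systemic rescue before the post-vaccination assessment (Protocol 16.1, SAP 5.4). As a robustness check, Protocol 16.4.3 repeats it on the ITT, "whereby any subjects without an evaluable vaccine response will be regarded as a Non-Responder". SAP 8.1.2 carries this forward: "Three sensitivity analyses will be performed on ITT population and the same statistical testing as the primary analysis will be performed". There, non-evaluable means that the endpoint cannot be classified because an assessment is missing. Never having been vaccinated is not distinguished from being vaccinated with no Week 16 sample.

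The ITT is everyone randomized (Protocol 16.1, SAP 5.3), and some of these subjects may not be vaccinated:

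- Protocol 9.7.1: "subjects who discontinue the study drug prior to Week 12 should not be vaccinated".
- Protocol 16.4.1: "Subjects in receipt of systemic rescue medication will not be vaccinated, and so will thus not be included in the mITT".
- Protocol 8.4.1: no vaccination after a subject becomes pregnant.

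The estimand table in SAP 3.1 lists no intercurrent event. The SAP index of tables repeats the missing-as-non-responder analysis for every binary secondary vaccine endpoint. The trial's aim on the difference is that the "90% confidence interval of the proportion difference between treatment groups will exclude a difference of more than 10" percent (Protocol 16.9).

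**The concern.** The study asks whether nemolizumab changes the response to a vaccine that was given (Protocol 5.4). An analysis that counts unvaccinated subjects as failures answers a different question, because its result also depends on how many subjects in each arm stayed on drug long enough to be vaccinated.

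Non-responder imputation is often taken to be conservative. That intuition comes from trials that aim to show a difference. Here the aim is to show that there is no important difference. Equal loss shrinks a true deficit toward zero. Heavier placebo loss shrinks it further or reverses it. Heavier nemolizumab loss creates a deficit that does not exist. At stake is how far agreement or disagreement between this table and the primary result can be read as evidence about robustness.

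**Working it through.** **The plan's own figure.** The 245 subjects (about 123 per arm) cannot be reproduced, because no power, response rate or dropout is stated. One set of assumptions comes close: 90% response in both arms, 80% power and one-sided 5% gives 112 per arm, or 125 with 10% dropout. The documents do not state that set.

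**Inputs from the documents.** 123 per arm, 1:1 allocation, 90% CI (SAP 6.1), 10-point limit (Protocol 16.9).

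**Assumed inputs.** Response among vaccinated subjects, q, and the share with an evaluable response, r, for placebo (P) and nemolizumab (N). Loss is taken as unrelated to response. The base case is a true 10-point impairment, q_P = 0.80 and q_N = 0.70.

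**Estimated quantity.** With non-evaluable subjects set to failure, the difference is

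d = r_N × q_N − r_P × q_P.

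For r_P = 0.80 and r_N = 0.90: d = 0.90 × 0.70 − 0.80 × 0.80 = 0.63 − 0.64 = −0.01. The true −10 points appears as −1.0.

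**Chance of passing.** This is an exact enumeration over two binomials of size 123 with success probabilities r × q, using an unstratified Wald 90% CI. Passing means that the lower bound is above −10 points.

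| Evaluable, placebo / nemolizumab | d (points) | Lower bound above −10 |
|---|---|---|
| 90% / 90% | −9.0 | 7% |
| 85% / 90% | −5.0 | 21% |
| 80% / 90% | −1.0 | 42% |
| 75% / 90% | +3.0 | 67% |

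Analysing only evaluable subjects in the same scenarios passes about 5% of the time throughout. For the three unequal-loss rows, 90% vs 80% response gives 26%, 54% and 80%, and 70% vs 60% gives 18%, 35% and 57%. A simulation with a two-stratum CMH-weighted difference (assumed 60/40 split) agrees closely, with 44% in the 80%/90% row.

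**Gap that erases the impairment.** Setting d = 0 with q_N = q_P − 0.10 gives r_P = r_N × (1 − 0.10/q_P). At r_N = 0.90:

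- q_P = 0.90: r_P = 0.80, a gap of 10 points.
- q_P = 0.80: r_P = 0.788, a gap of 11 points.
- q_P = 0.60: r_P = 0.75, a gap of 15 points.

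**Both-bounds reading.** If both bounds must lie within 10 points of zero, the interval itself is limiting. In the 80%/90% row the half-width is 1.645 × √(0.63 × 0.37/123 + 0.64 × 0.36/123) = 10.1 points, so the interval rarely fits. The pass rate is about 1% there, at most 2% for the 80% vs 70% pair, and at most about 9% for 90% vs 80%.

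**Reverse case.** No true effect (80% response in both arms), evaluable 90% placebo and 80% nemolizumab: d = 0.64 − 0.72 = −8 points. The 90% CI excludes zero in 39% of trials (nominal 10%). The lower bound clears −10 points in 10%, against 57% among evaluable subjects.

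**The case against.** A reader might infer that the trial could declare no impairment when a 10-point impairment exists. The documents do not support that. The conclusion rests on the mITT analysis, and no section gives the ITT check a decision role. In simulated trials with 80% vs 70% response, both analyses pass together in only 4.8% to 5.0% of trials across the three unequal-loss scenarios. The primary analysis fails about 95% of the time and would disagree with the check.

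A reader might also infer that placebo loss will be heavier. The documents make that plausible but do not show it. Protocol 5.3.1 describes benefit on AD in earlier studies, and Protocol 8.4 lists treatment failure and systemic rescue among the reasons to stop drug. Against this, the only loss figure is overall: 60 of 70 completed the prurigo nodularis study, so 14.3% did not. Discontinuation for adverse events there was similar between arms. Protocol 5.3.1 also names AD exacerbation as a potential nemolizumab risk. Topical rescue and phototherapy do not forfeit vaccination (Protocol 9.6.1.3), which narrows the route from poor AD control to non-vaccination.

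Three further objections have force. The larger pass rates need a one-sided reading that the plan does not spell out. Much of the reporting exists: SAP 10.1 counts vaccine recipients by arm, and SAP 7.1 gives discontinuation reasons. The all-ITT analysis is also the one planned analysis that keeps every randomized subject in the denominator, so deleting it would lose information.

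What remains is narrower. The check does not isolate vaccine response. Neither the observed-case nor the COVID-19 analysis imputes a missing result after vaccination, so neither fills that gap.

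**Conclusion.** The point holds as a limit on what this sensitivity analysis can show. It estimates a composite of being vaccinated, being sampled and responding, and it is not conservative for a no-impairment conclusion. The primary result is not biased by it.

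The size depends on the loss pattern. With equal 10% loss the distortion is small (7% against about 5%). A 10-point gap in the evaluable share moves the estimate by 9 points at 80% vs 70% response and can make the check agree or disagree for reasons unrelated to the vaccine. The figures rest on assumed response and loss rates, loss unrelated to response, and, for the pass rates above 9%, a criterion on the lower bound alone. The shift in the estimate does not depend on how the criterion is read. This is an inexpensive improvement to interpretation and does not threaten the trial's main conclusion.

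**What to change.** - Keep the all-ITT non-responder analysis. In SAP 8.1.2 and Protocol 16.4.3, label it a composite of being vaccinated and responding, and state that it does not by itself support or overturn the 10-point conclusion.
- Add to SAP 8.1.2 a non-responder analysis among randomized subjects who received the relevant vaccine (Tdap for the tetanus endpoints, MCV4 for the SBA endpoints), with a missing Week 16 result set to non-responder. Place it beside Table 14.2.1.1.2 and the matching missing-as-non-responder tables for the secondary vaccine endpoints.
- Show the reason not vaccinated, by arm, next to the vaccination counts already planned in SAP 10.1.

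The cost is SAP wording, a population flag and one extra table per endpoint. Vaccine administration is already recorded and listed. The downside is that the added analysis conditions on reaching vaccination, as the mITT does, so it is not a comparison of all randomized subjects. The retained all-ITT table and the by-arm reasons show how much that matters.
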